Consented subjects who meet inclusion and exclusion criteria will start ketamine infusion at 5mcg/kg/min for one hour after which the infusion rate will be increased to 10mcg/kg/min for another hour. At the end of the 2 hours, ketamine infusion will be discontinued. The ketamine dose used in the study is within the recommended range per MGH intravenous drug policy for intubated patients. A trial of spontaneous breathing (SBT) with PEEP=0 and no pressure support for 1 minute will be performed at 3 specific times - prior to initiation of ketamine, 1 hour post infusion of at 5mcg/kg/min and 1 hour post infusion at 10 mcg/kg/min. During these times, respiratory function measurements will be made (see below). Subjects who pass the SBT and can be extubated prior to enrollment or subjects who pass the SBT with a plan to extubate will not be included.

Measurement of respiratory function

Respiratory flow will be measured using a pneumotach (Hans Rudolph Inc., Shawnee, KS) connected to the ventilation tubing of the patient during the spontaneous breathing trials. Inspiratory flow, tidal volume, and minute ventilation, as well as respiratory rate and duty cycle (inspiratory time/total time of respiratory cycle) will be measured.

Measurement of arousal state and respiratory effort

Electroencephalography (EEG)-based arousal state and respiratory effort will be continuously measured in all subjects using the the Sedline brain function monitor (Masimo Corporation, Irvine, CA), as shown in a previous study.¹⁶ The measurement will start prior to initiation of ketamine and continued until 3 hours after the end of ketamine infusion.

Measurement of esophageal pressure

A standard nutritional nasogastric tube with an integrated esophageal balloon or an esophageal balloon catheter will be inserted if not already in place by a trained physician or respiratory therapist prior to initiation of ketamine and will be used for measurement of transpulmonary pressure for the study period

(approximately 5 hours). The correct positioning will be checked by changes of waveforms when withdrawn from the stomach into the esophagus and by the occlusion test.

Measurement of CO₂ monitoring

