There is a potential risk of using the nasogastric tube, which includes nasopharyngeal or esophageal injury or perforation, aspiration, and discomfort. Inserting the nasogastric tube may be uncomfortable and could cause gagging or even vomiting, and a minimal risk of bleeding. The risk of discomfort will be minimized by maintaining subjects on propofol and hydromorphone or morphine. The subjects will have a tube in his/her esophagus and a secured airway with an endotracheal tube. The risk of aspiration will be minimized by having an experienced respiratory therapist or attending physician perform the procedure. The tube, once in place, does not induce the subject's gag reflex. The NGT has been demonstrated to provide successful, safe, and reliable NGT insertion without any side effect for obese patients by a prior study.

Risks associated with low dose ketamine use include hypertension, hypotension, tachycardia, bradycardia, and transient signs of emergence symptoms (confusion, adverse psychiatric symptoms). Adverse effects of ketamine are dose dependent and incidence of emergence symptoms are significantly less (<5%) with low dose ketamine. Subjects will also be on propofol which will further reduce the risks of emergence.

VIII. Potential benefit

Patients don't have a direct benefit by participating in the study. Information gathered from this study may help future patients receive optimal ketamine efficacy and safety monitoring.

IX. Monitoring and quality assurance

[figure not shown]
Patients will have sedation, pain and CAM-ICU assessed on a daily basis as part of routine ICU care. Patients will have respiratory rate assessed while they are on ketamine infusion as a standard of care in the ICU. Principle investigator will review the safety/efficacy data daily. Additionally, a physician investigator will review all hemodynamic monitoring pertinent to ketamine treatment. The principal investigator and study staff will meet after each time five subjects are enrolled to review data to ensure validity, adherence to IRB-approved protocol, patient ethics, security and confidentiality of protected health information, and submission of safety reports.

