During ketamine infusion, if the patient develops hemodynamic instability (i.e., mean arterial pressure (MAP) change by $\pm 25\%$ from baseline, heart rate more than 150 bpm or less than 50 bpm, or parameters otherwise defined by the primary team) and this instability is perceived to be associated with ketamine use, the ketamine infusion will be stopped and the patient will be withdrawn from the study.

All adverse events (AEs) will be reported. AEs are defined as any unfavorable and unintended sign, symptom, or disease temporally associated with ketamine therapy. The relationship of any AE(s) to ketamine therapy will be assessed by the clinician and reported as not related, unlikely, possibly, probably, or definitely related, and the intensity of the AE(s) as mild, moderate, or severe.

The PI will report adverse events or other unanticipated problems to the PHRC as described in the PHRC policy on Adverse Event Reporting and Unanticipated Problems Involving Risks to Subjects or Others.

[figure not shown]
Overview of study procedures:

Note: Ketamine infusion is discontinued at 2 hours and the subsequent decrease in ketamine plasma concentration is due to the natural drug elimination from the system.

1. Supplementary Figures

Figure S1. Method of assessment of respiratory timing

This figure illustrates how respiratory timing (i.e. inspiratory-to-expiratory (I:E) ratio, inspiratory time/total respiratory cycle time (T_i/T_{tot})) was analyzed. Inspiration and expiration were defined based on flow. Data was analyzed using a spirometry algorithm that was developed based on the Spirometry add-on function (Spirometry Version: 2.5.4) in LabChart, which automatically detected zero flow periods to identify transitions between inspiratory and expiratory phases. Flow channel was filtered using a low-pass 1 Hz

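### The adverse-event definition and relatedness scale in Section IX refer only to ketamine, so harms from the study's catheter insertion and unsupported breathing trials can go uncounted or cannot be attributed to the procedure

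*Combined protocol and SAP*

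**What the plan says.** Section IX (Monitoring and quality assurance) promises that all adverse events will be reported and then defines the term: "AEs are defined as any unfavorable and unintended sign, symptom, or disease temporally associated with ketamine therapy". On causality it says: "The relationship of any AE(s) to ketamine therapy will be assessed by the clinician and reported as not related, unlikely, possibly, probably, or definitely related". No second scale is given for any other study component.

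Section V (Study procedures) adds two kinds of non-drug exposure:

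- **Esophageal catheter.** It "will be inserted if not already in place by a trained physician or respiratory therapist prior to initiation of ketamine", and it "will be used for measurement of transpulmonary pressure for the study period". Transpulmonary pressure is a secondary endpoint in Section II.
- **Unsupported breathing trials.** "A trial of spontaneous breathing (SBT) with PEEP=0 and no pressure support for 1 minute will be performed at 3 specific times", namely "prior to initiation of ketamine, 1 hour post infusion of at 5mcg/kg/min and 1 hour post infusion at 10 mcg/kg/min". Section III notes that SBT timing and pressure support were changed from clinical practice for the study.

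Section VII (Risk and discomfort) lists the catheter's risks as "nasopharyngeal or esophageal injury or perforation, aspiration, and discomfort", and adds gagging, vomiting and a small risk of bleeding. It names no risk for the breathing trials.

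**The concern.** The study exposes subjects to ketamine, to an invasive catheter and to short periods without ventilatory support. The adverse-event rule is built around the first of these only. Two consequences follow from the wording.

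First, an event at catheter insertion or at the baseline breathing trial occurs before any ketamine has been given. A site that reads the definition literally can leave it off the adverse-event record.

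Second, an event that is recorded has only one causal question asked of it. A nosebleed from the catheter that shows during infusion, or a desaturation at a later breathing trial, can be graded as unrelated to ketamine, with no entry showing what did cause it. It can also be graded as possibly related, which charges a procedural harm to the drug. The first error hides a cost of the research procedures. The second distorts the ketamine safety record.

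Section VIII says that subjects gain no direct benefit from taking part. Harms that arise only because of research measurements are therefore ones the trial should be able to count.

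**Working it through.** The plan states no figure on this point, so there is none to reproduce. The check sets each study step against the two parts of the Section IX rule.

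| Step (Section V) | Timing | Inside the definition? | Attributable to the procedure? |
|---|---|---|---|
| Catheter insertion, if none in place | Before ketamine | Not on a literal reading; temporal association is undefined | No |
| Baseline SBT, PEEP 0, no pressure support | Before ketamine | Not on a literal reading | No |
| SBT after the hour at 5 mcg/kg/min | During ketamine exposure | Yes | No |
| SBT after the hour at 10 mcg/kg/min | During ketamine exposure | Yes | No |
| Catheter harm that first shows during infusion | During ketamine exposure | Yes | No |

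The third column depends on how temporal association is read. The fourth does not: the only relationship asked for is the one to ketamine.

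**Number of occasions**, taking the planned 15 subjects and assuming that all complete the session:

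- Baseline SBTs before ketamine: 15 × 1 = 15.
- SBTs during ketamine exposure: 15 × 2 = 30.
- Catheter insertions for the study: 0 to 15, because the documents do not say how many subjects will already have a suitable tube.
- Procedures before ketamine in total: 15 + 0 = 15 up to 15 + 15 = 30.

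**What one event means at this size.** One event in 15 subjects is 1/15 = 6.7%. With no events in 15, the exact one-sided 95% upper bound is 1 − 0.05^(1/15) = 18.1%. The chance of at least one procedural harm is 1 − (1 − p)^15. For assumed per-subject rates p of 1%, 2% and 5% it is 14%, 26% and 54%. The documents give no procedural rate. These figures show only that a single event matters in so small a trial; they do not measure how many events the rule would lose.

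**Whether other text closes the gap.** Section IX also sends adverse events and other unanticipated problems to the PHRC under its own policy. On plain wording, catheter harms listed in Section VII are anticipated, so it is unclear that this route covers them. The policy is not in the documents and may be broader. Even then, it would not put a procedural relationship into the trial's own adverse-event record.

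**The case against.** Several counter-arguments have force.

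- **Timing is not fixed.** The definition does not say that an event must follow the start of infusion. A generous reader could include an event shortly before it, and a catheter injury that shows during infusion is captured on any reading. This stands: the right claim is that harms can be missed. A reader might infer that everything between insertion and infusion is excluded, but the wording does not go that far.
- **Most breathing trials are covered.** Two of the three take place during ketamine exposure, so events there must be reported. This stands. Nor would such events necessarily be coded not related; a clinician could rate them possibly related. For these trials the gap is in attribution only.
- **Oversight is wider than the definition.** A reader might infer that the principal investigator would not see a procedural signal in time to act. The documents do not support that. Section IX has the principal investigator review safety and efficacy data daily, without limiting this to ketamine, and a data review follows every five subjects. Section VII describes close contact with the care team and removal of devices on request or when clinically necessary. An unlabelled event is not necessarily an unseen one.
- **The added exposure may be small.** MGH's clinical SBT already uses no PEEP and no pressure support for 30 minutes, so one minute adds little there. At BIDMC the clinical trial uses 5 cmH₂O of pressure support, so the argument does not carry over.
- **There is no safety endpoint.** All listed outcomes are physiological or EEG measures, so no planned analysis is biased. What is affected is the adverse-event record.

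A figure in Section IX is missing from the text reviewed, so statements about what that section omits carry some caution. None of these points supplies a relationship category for study procedures.

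**Conclusion.** The point holds as a defect in a stated rule. Followed as written, Section IX can leave out harms from catheter insertion and the baseline breathing trial, and it provides no way to attribute any recorded harm to a study procedure. The first part rests on a literal reading of temporal association with ketamine; the second holds on any reading.

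The gap in attribution applies to all 15 planned subjects, as does the possible gap in capture at the baseline breathing trial. The possible gap in capture at catheter insertion applies to between 0 and 15 subjects. The documents do not allow an estimate of how many events would be lost or misattributed. The PHRC route may cover some of them, which cannot be checked without the policy.

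The primary analysis of inspiratory flow is not affected. The change should be made because the protocol itself foresees the catheter harms and the correction is small.

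**What to change.** In Section IX:

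1. Keep the existing description of what kind of event counts, but start collection at the first study procedure (catheter insertion or baseline SBT, whichever comes first) and run it to the end of study observation. Require temporal association with ketamine **or any study procedure**.
2. Have the clinician grade relationship separately to (a) ketamine and (b) study procedures, using the existing five categories for each.

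The cost is a wording change, one more field on the adverse-event form, and probably more minor procedural events reported. No dose, schedule, measurement or clinical rule changes.
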